Design Considerations. Mobile phones—access and confidentiality. Participants will need their own phones to enroll in the study. Participants are advised to password-protect their phones if possible yet many do not have this option. We will therefore (a) never send messages with identifying information or directly refer to HIV or HIV treatment, and (b) only enroll YPLH who agree to the risk of game messages being seen by others who use their phone. Phone numbers and de-identified patient information is securely stored in a HIPAA- compliant cloud database hosted by Dimagi. Only select study staff will be able to link participant names with ID numbers. Information will be stored and destroyed following HIPAA and IRB procedures (see Protection of Human Subjects). Assessments: Assessments will take 1 hour to complete and be administered in a private room in the Clinic using ACASI at baseline and 6- and 12-months post-baseline. Clinic records will also be coded for biologic outcomes and clinic visits at these

assessments. Participants will be remunerated 40 Cedis (\$8) for each one. They will also be given 80 Cedis worth of prepaid phone credits to send and receive text messages at the baseline and first follow-up assessments.

Measures: The measures below will evaluate HIV-related health functioning, knowledge, attitudes, and behavior. Measures previously used in Ghanaian or SSA

adolescent or young adult samples were chosen when possible. If necessary, revisions to measures will be made based on formative work to ensure cultural relevancy. **Primary**

Outcomes: Past 30-day adherence will be assessed using a 3-item measure recently developed via intensive cognitive interviewing and field tests (47) and validated against electronic drug monitoring(48) . Self report of four day ART adherence based on percent of doses taken will also be assessed using the AACTG questionnaire (49). Staff will abstract from the clinic record number of medical visits kept and missed in the past 6 months(50), and most recent HIV viral load measurement, CD4 count, and current ART schedule. See Appendix 2 for data extraction form. If viral load was not measured in the past 3 months, it will be assessed at this visit as part of routine clinical care. **Secondary**

[figure not shown]
Outcomes: Figure 5 presents an assessment schedule for each aim and describes the secondary outcomes. Appendix 3 contains questionnaire.

Data Analytic Plan

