The findings from each phase of this study will be disseminated. Planned manuscripts include (1) a process analysis of our Text-Based Adherence Game using findings from the iterative open trial and youth advisory board meetings; (3) a study which presents descriptive quantitative data from our baseline sample of randomized pilot YPLH participants; and (4) the results from the randomized pilot testing the longitudinal effects of our Text-Based Adherence game on biobehavioral outcomes. Presentations will be submitted for dissemination at conferences including the meeting of the International AIDS Society. In addition, findings from our randomized pilot will be reported on <https://clinicaltrials.gov/>, a national (U.S.), freely-accessible registry which catalogues the results of publicly funded clinical trials. Finally, after each phase of the study, a one-page summary of the results will be written in plain language and offered to participants during their routine clinic appointments.

ETHICAL ISSUES

Participant Involvement

Participant involvement is needed to accomplish each Specific Aims 1-2: Aim 1 involves semi-structured interviews and quantitative data collection with YPLH (n = 24) following their participation in an open trial of the intervention to gauge feasibility and satisfaction. Ten of these participants will also complete quantitative self-report measures of primary and secondary study outcomes pre- and post-trial. In addition, a youth advisory board consisting of YPLH will meet with investigators three to five times to review aid in intervention development. *Finally, as part of a separate component of the Development Phase focused on adolescents living with (ALH; ages 12-17), ALH (n= 12-16) and parents of ALH (n= 12-16) will participate in focus groups, and 10 parent-ALH dyads will participate in cognitive interviews.* Aim 2 involves a randomized controlled pilot (n=60) of the intervention which includes quantitative self-report assessments and clinic chart review at baseline, 6 months, and 12 months post-baseline with YPLH.

Data Storage and Protection

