Appendix 2: Chart Review Data Abstraction Form

1) Today's date:
(MM)_____(DD)_____(YY)_____

2) Date of first presentation to KBTH:
(MM)_____(DD)_____(YY)_____

3) Age (years) _____

4) Gender
 1 – Male
 2 – Female

5) Marital Status
 1 – Single
 2 – Married
 3 – Divorced
 4 – Separated
 5 – Cohabiting
 6 – Not Available

6) Highest education level attained
 1 – None
 2 – Primary
 3 – JSS
 4 – MSLC
 5 – Sec/Tech
 6 – University

7) Employment/occupation at presentation

8) Employment status at presentation
 1 – Full time
 2 – Part time
 3 – On leave
 4 – Unemployed
 5 – Unknown

9) Dependent children (aged <18 years)
 1 – Total number

 2 – How many are HIV+

10) Funding type
 1 – Patient out-of-pocket
 2 – Medical insurance
 3 – Special project
 4 – Employer sponsored
 5 – Unknown
 6 – Other: _____

11) HIV status at presentation:
 Known positive
 Diagnosed at admission

12) Current WHO stage
 1 – Stage I
 2 – Stage II
 3 – Stage III
 4 – Stage IV

13) Current Drug Therapy (check all that apply):
 1 – Stavudine
 2 – Zidovudine
 3 – Lamivudine
 4 – Abacavir
 5 – Tenofovir
 6 – Didanosine
 7 – Nevirapine
 8 – Efavirenz
 9 – Combivir (zidovudine and lamivudine)
 10 – Kaletra (lopinavir/r)
 11 – Nelfinavir
 13 – Other:

14) Most recent CD4 cell count: _____

15) Date of most recent CD4 cell count test:

16) Most recent viral load: _____

17) Date of most recent viral load test:

18) Detectable viral load in past six months:
 – Yes
 – No

19) Date of ART initiation:
(MM)_____(DD)_____(YY)_____

20) Number of clinic appointments missed in the past 6 months

21) Number of clinic appointments kept in the past 6 months

22) Number of clinic appointments missed in the past 12 months

23) Number of clinic appointments kept in the past 12 months

24) Longest period without an appointment (months):

25) Route of HIV infection
 1 – Perinatal
 2 – Behavioral
 3 – Unknown

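### In the readable text, follow-up CD4 is the latest chart value with no date limit, so a CD4 drawn before randomisation can be entered as the 6- or 12-month outcome

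*Combined protocol and SAP*

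**What the plan says.** The pilot has a baseline and two follow-up assessments, at 6 and 12 months. Under Assessments: "Clinic records will also be coded for biologic outcomes and clinic visits at these" assessments. Participant Involvement confirms "clinic chart review at baseline, 6 months, and 12 months post-baseline with YPLH".

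Under Measures, Primary Outcomes, staff take from the record the visits kept and missed "and most recent HIV viral load measurement, CD4 count, and current ART schedule". Shortly after comes a recency rule that names one test only: "If viral load was not measured in the past 3 months, it will be assessed at this visit as part of routine clinical care".

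The Chart Review Data Abstraction Form (Appendix 2) follows the same approach. Item 14 is "Most recent CD4 cell count" and item 15 is "Date of most recent CD4 cell count test".

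In the Data Analytic Plan, Hypothesis Two expects higher CD4 in the game arm at 6 and 12 months. Each outcome is tested by repeated measures ANCOVA, and missing data are multiply imputed. No readable sentence says how old a follow-up CD4 may be or what the item 15 date is used for.

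**The concern.** A CD4 drawn before randomisation cannot carry a treatment effect. Under the collection rule it is still a valid entry at 6 or 12 months whenever no later test exists. For that participant the follow-up value is a pre-randomisation value, and the recorded change says nothing about the game.

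The entry is filled, not blank, so multiple imputation is not triggered. The analysis would treat the value as an observed outcome, and the CD4 comparison in Hypothesis Two would be pulled towards no difference. The pilot looks only for an early sign of impact, and a diluted CD4 effect weakens that sign.

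**Working it through.** **1. Text, side by side.** Viral load: latest value, but retested if older than 3 months. CD4: latest value, no age limit, no retest. The form records the CD4 date, and no readable rule acts on it. The questionnaire's self-reported CD4 (Physical Health section) also asks for the latest result without a date, so it does not fill the gap.

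**2. The plan's own sample figure.** 60 × 0.86 = 51.6, which rounds to the stated 52. Equal allocation (assumed; no ratio is stated) gives 26 per arm.

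**3. Formula.** Let τ be the true CD4 effect, μ the CD4 change common to both arms, and s_g and s_c the shares of follow-up values in the game and control arms that predate randomisation. Mean change is (1 − s_g)(μ + τ) in the game arm and (1 − s_c)μ in the control arm, so

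expected difference = (1 − s_g)τ + (s_c − s_g)μ.

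With equal shares this is (1 − s)τ.

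**4. How large s could be.** The documents give no CD4 testing frequency. Assume each participant is tested every T months with evenly spread timing. The share of values at month m that predate randomisation is max(0, 1 − m/T). The share of month-12 values that repeat the month-6 value is max(0, 1 − 6/T) − max(0, 1 − 12/T).

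| T (months) | Pre-randomisation at month 6 | Pre-randomisation at month 12 | Post-randomisation value filling both waves |
|---|---|---|---|
| 6 | 0% | 0% | 0% |
| 9 | 33% | 0% | 33% |
| 12 | 50% | 0% | 50% |
| 18 | 67% | 33% | 33% |

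**5. Effect of equal staleness.** Assumed: τ = 0.5 SD, μ = 0, 26 per arm, single-visit ANCOVA, baseline correlation r of 0.5, 0.7 or 0.9; 6,000 simulated trials each, stale values kept.

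| s | (1 − s) × 0.5 | Simulated mean effect | Coverage of the 95% interval |
|---|---|---|---|
| 10% | 0.45 | 0.45 | 93–94% |
| 25% | 0.375 | 0.38 | 81–91% |
| 50% | 0.25 | 0.25 | 32–73% |

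In terms of power, take a single-visit comparison of two means that has 80% power at 26 per arm (d = 0.78, two-sided 5%, SD held fixed). Power falls to 71% at s = 10%, 61% at 20%, 50% at 30% and 29% at 50%.

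**6. Both visits averaged, annual testing, constant effect.** Month 6 contributes 0.5 × 0.50 = 0.25 and month 12 contributes 0.50, so the average is (0.25 + 0.50)/2 = 0.375 SD. Simulation gives 0.37–0.38 SD with coverage 76–90%.

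**7. Unequal staleness, no true effect.** With 35% stale in control, 25% in the game arm and μ = ±0.5 SD, the spurious difference is (0.35 − 0.25) × (±0.5) = ±0.05 SD. Simulation gives 0.046 to 0.050 SD in either direction.

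**The case against.** **Unseen text.** Figure 5 is described as the assessment schedule, which is where a CD4 timing rule would naturally sit. It could not be read, nor could Figure 4 (the pilot's steps). Text after the title page and under the Data and Safety Monitoring Plan heading was also unavailable. A reader might infer that the plan has no CD4 window at all. The documents support only the narrower statement that none appears in the readable text.

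**The form.** Appendix 2 has look-backs for "Detectable viral load in past six months" and for appointments, such as "Number of clinic appointments missed in the past 6 months". A reader might infer that the form dates every chart outcome except CD4. It does not. Appointment items are counts, which need a period. The detectable-viral-load item plausibly serves the pilot's entry criterion. Item 16, the viral load value itself, is worded as openly as the CD4 item. The contrast that carries weight is the 3-month sentence under Primary Outcomes.

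**The date is collected.** Item 15 lets an old value be found later. That makes the remedy cheap, but it does not supply a rule. Without one, the choice to keep or drop old values would be made after the data are seen.

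**Size.** No testing frequency is given, so the harm may be nil. The worst coverage figures come from r = 0.9, where 0.5 SD equals 0.5/√(1 − 0.81) = 1.15 residual SD. That is a large effect for a pilot that disclaims adequate power. At r = 0.5–0.7 and s = 25%, coverage is 89–91%. This criticism stands.

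**False signals.** A reader might infer that stale values create spurious CD4 findings. With equal shares they do not: simulated type I error stayed between 0.037 and 0.057. Unequal shares could arise if CD4 testing follows clinic attendance, which Hypothesis Two expects to differ, but no readable text links the two. Even then each 10-point gap adds only 10% of the common CD4 change.

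**Conclusion.** The point holds as a gap in a stated rule. Followed as written, the readable text lets a pre-randomisation CD4 stand as a follow-up outcome, and such a value is never imputed. With equal stale shares the expected CD4 effect is (1 − s) of its true size.

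How often this happens cannot be determined from the documents. Under evenly spread tests, s is zero for six-monthly or more frequent testing. At 10% the loss is small (0.45 instead of 0.50 SD). It becomes material if testing is annual or rarer. All values of s, T, r, τ and μ are assumptions. It would go too far to say that the trial's CD4 results are biased.

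The scope is CD4 alone. CD4 stands under Primary Outcomes but is absent from the outcomes listed in Aim 2, and viral load, the biologic outcome named there, already has a recency rule. The rule is worth settling before analysis because the remedy is inexpensive. If unseen text already sets a CD4 window, the point falls.

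**What to change.** Before analysis, add one data-handling rule based on item 15:

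- Set to missing any 6- or 12-month CD4 dated on or before randomisation.
- Handle it by the planned multiple imputation, with attendance (items 20–24) and viral load in the imputation model.
- Report by arm the number of values excluded and the age of the CD4 values used.
- Where one post-randomisation CD4 fills both waves, flag it. Add a sensitivity analysis that counts it only at the wave whose interval contains its date (randomisation to the 6-month assessment, or from there to the 12-month assessment).
- If Figure 4, Figure 5 or other text already gives a CD4 window, apply that and say so.

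The viral load limit should not simply be copied to CD4. With no CD4 retest, a 3-month look-back would discard 1 − 3/T of values, including valid post-randomisation ones: 50% at six-monthly, 67% at 9-monthly, 75% at annual and 83% at 18-monthly testing.

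**Cost.** No new blood draw and no new form item. The cost is missing CD4 values, in the pre-randomisation shares tabulated in step 4 of the working. Annual testing would leave 26 × 0.50 = 13 observed values per arm at month 6 and all 26 at month 12. 18-monthly testing would leave about 26 × 0.33 ≈ 9 and 26 × 0.67 ≈ 17. Before imputation, the sample-size factor at a visit is about 1/(1 − share removed), so 2.0 at month 6 under annual testing. The interval rule would remove 33%, 50% and 67% of month-12 values under 9-monthly, annual and 18-monthly testing, which is why it belongs in a sensitivity analysis.

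Imputation removes the bias only if staleness is unrelated to CD4 given the variables in the model. In a simulation with 25% stale in both arms, staleness tied to attendance in the control arm only and a true effect of 0.5 SD, keeping stale values gave 0.25–0.35 SD. Setting them to missing without using attendance gave 0.33–0.46 SD, and imputing with attendance gave 0.50–0.51 SD. That last result holds because attendance fully explained staleness by construction.

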Measures: Participants' overall satisfaction with the game will be assessed using a modified version of the Client Satisfaction Questionnaire (CSQ-8) after each iteration. The CSQ is an 8-item measure with good reliability and validity and used previously with African samples (46). They will also complete a modified Session Evaluation Form (SEF), which has 13 items that reflect areas of feasibility and intervention utility. Participants will complete measures of main study outcomes using an audio-assisted computer self-interview (ACASI). Main outcome measures are listed in the next section. The last prototype will be reviewed and revised by the research team before being finalized. **Training of Research Assistants (RAs), Fidelity Monitoring, and Supervision:** RAs will be trained by the co-PI ([name]) over a period of two days to provide

game instructions. Game instructions will be audio-recorded and coded for fidelity. Problems with fidelity will trigger retraining of RAs by the PI. Peer educators will receive in-person supervision from study staff who will themselves receive Skype supervision from the [name]. [name] will also monitor participants' game activity daily via the system's website.

Randomized Controlled Pilot Phase (Aim 2)

We will evaluate the preliminary impact of the Text-Based Adherence Game run for one year compared to a control group. The pilot will include 60 YPLH on ART with the same eligibility criteria as the open trial. The same procedures will also be used pending open trial feedback. The game will be evaluated via a baseline and two follow-up assessments (6-/12-months post-baseline). Randomization will occur after enrollment using a random number generator. Participants not randomized to the Text-Based Adherence Game will receive the SOC condition as described above. See Figure 4.

Figure 4. Steps for Aim 2 Randomized Controlled Pilot

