Hypothesis One (Aim 1). The Text-Based Adherence Game will be feasible, appealing, and useful. YPLH in the third open trial iteration of the Text-Based Adherence Game will show shifts in primary and secondary outcomes in the expected directions from pre-post assessments.

Hypothesis Two (Aim 2). Compared to participants in the control group, participants in the Text-Based Adherence Game will show at 6 and 12 months post-intervention: improved ART adherence, clinic attendance, biologic functioning (lower

Figure 5. Assessment Schedule

HIV viral load, higher CD4 count), and shifts in secondary outcomes (social support, self-efficacy, etc.) consistent with adherence promotion. Repeated measures ANCOVAs will be used to test differences over time between study conditions on each outcome variable. Missing data will be handled using multiple imputation. Potential imbalance between treatment conditions on baseline characteristics will be addressed using inverse probability of treatment weights (51). Power: As this is a pilot study and the impact of the intervention is not known, there may not be adequate power to determine its efficacy; also, pilot studies are not designed to provide accurate estimates of effect sizes upon which to base large trials(52). However, the small pilot may provide a “signal” of impact on its primary outcomes and we will examine the effects of the intervention on secondary outcomes based on Social Action Theory. We assume that retention over one year is at least 86% based on past studies conducted in Ghana (31, 53) thus 52 cases of the 60 enrolled in the pilot are available for analysis. Power analyses were run with G*Power 3(54). The model assumed 3 assessments with 52 individuals. The analyses with alpha of 0.05 and power 0.80 will be able to detect small to medium effects.

DISSEMINATION OF RESULTS

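### Baseline imbalance in a randomised pilot of 60 is to be handled by inverse probability of treatment weights with no stated standard error method; entering prespecified covariates in the planned ANCOVA would be simpler, calibrated and slightly more precise

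*Combined protocol and SAP*

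**What the plan says.** The Data Analytic Plan, Hypothesis Two (Aim 2), sets the outcome model: "Repeated measures ANCOVAs will be used to test differences over time between study conditions on each outcome variable". On baseline differences it adds: "Potential imbalance between treatment conditions on baseline characteristics will be addressed using inverse probability of treatment weights (51"). On missing data: "Missing data will be handled using multiple imputation". The section on the Randomized Controlled Pilot Phase says: "Randomization will occur after enrollment using a random number generator".

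The plan does not say:
- which baseline characteristics enter the weights, or what triggers weighting;
- whether the weights are stabilised or truncated;
- how the standard error is computed;
- how weights and imputations are combined;
- which covariates are in the ANCOVA.

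The paper cited for the weights concerns, by its title, marginal odds ratios in small samples.

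**The concern.** Randomisation already removes systematic confounding at baseline. Weights can then only rebalance chance differences, and they need a second estimated model (the propensity score) fitted to 52 to 60 people. The ANCOVA can make the same correction with the covariates on its right-hand side.

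Two consequences follow at this sample size. The weighted estimate is somewhat noisier. And the standard error that a weighted model prints by default ignores that the weights were estimated, so it does not track the estimate's real variability. The pilot seeks only a signal of effect to support an application for a larger trial. A miscalibrated interval could hide that signal or exaggerate it.

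**Working it through.** **The plan's own figure.** 60 × 0.86 = 51.6, which rounds to the plan's 52 ("thus 52 cases of the 60 enrolled in the pilot are available for analysis"). The plan also says: "The analyses with alpha of 0.05 and power 0.80 will be able to detect small to medium effects". It gives no numeric effect size or correlation. Using the noncentral F with N = 52, m = 3 assessments and an assumed correlation ρ of 0.3, 0.5 and 0.7:
- Group-by-time interaction, λ = f²Nm/(1−ρ): detectable f is 0.21, 0.18 and 0.14.
- Between-group effect, λ = f²Nm/(1+(m−1)ρ): detectable f is 0.29 to 0.35.

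The claim is met for the interaction only, so there is little precision to spare.

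**Simulation inputs.** From the documents: N = 52 or 60, randomised, ANCOVA, two-arm weights. Assumed: 1:1 simple randomisation, normal outcomes with SD 1, one follow-up mean per person, baseline-outcome correlation 0.5, and k covariates explaining a share R² of outcome variance. There were 4,000 trials per setting, so the Monte Carlo standard error at 5% is √(0.05 × 0.95/4000) = 0.34 percentage points.

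**Estimators.** The propensity e is a logistic regression of arm on the baseline outcome and covariates. The weight is w = a/e + (1−a)/(1−e). *Weighted* is weighted least squares on arm and baseline outcome, with the default model standard error. *Direct* is unweighted ANCOVA on arm, baseline outcome and the same covariates.

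| N | k | R² | True SD, direct | True SD, weighted | Ratio | Weighted SE ÷ true SD | Type I, weighted | Type I, direct |
|---|---|---|---|---|---|---|---|---|
| 52 | 5 | 0 | 0.2577 | 0.2632 | 1.021 | 0.902 | 7.5% | 5.0% |
| 52 | 5 | 0.2 | 0.2199 | 0.2262 | 1.029 | 1.050 | 4.0% | 4.9% |
| 52 | 5 | 0.4 | 0.1753 | 0.1874 | 1.069 | 1.268 | 1.3% | 4.5% |
| 52 | 8 | 0.2 | 0.2302 | 0.2458 | 1.068 | 0.967 | 5.3% | 4.7% |
| 60 | 5 | 0.2 | 0.2051 | 0.2103 | 1.025 | 1.059 | 3.9% | 5.4% |
| 60 | 8 | 0.2 | 0.2077 | 0.2183 | 1.051 | 1.014 | 4.1% | 4.6% |

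A separate simulation with 3 to 8 covariates and R² of 0.05 to 0.4 agreed. The true SD was about 1 to 8% smaller for direct adjustment, and the default weighted standard error ran from about 10% too small to 35% too large.

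**Why the default standard error misses.** At N = 52 with 5 covariates, the weighted model reports a mean standard error of 0.2375, 0.2375 and 0.2377 at R² = 0, 0.2 and 0.4. The true SD falls from 0.2632 to 0.2262 to 0.1874. The reported figure gives no credit for the covariates. More data do not cure this: at N = 2000 the two estimators have the same SD (0.0299), but the default weighted standard error is still about 30% too large.

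**Power at a difference of 0.6 SD, N = 52, 5 covariates.**
- R² = 0.2: direct 74%; weighted 69% with the default standard error, 64% with a sandwich that treats the weights as known.
- R² = 0.4: direct 92%; weighted 74% and 68%.

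Most of this loss comes from the reported standard error. At R² = 0.4 it is 0.2377/0.1759 = 1.35 times the direct one, while the true SD is only 1.07 times as large.

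**Other ways to get the inference, N = 52 to 60 (bootstrap and permutation at N = 52 only).**
- Sandwich with weights treated as known: type I error 0.8 to 6.2%.
- Stacked sandwich allowing for estimated weights: 5.5 to 9.2%.
- Bootstrap: standard error 6 to 24% too large, type I error 1.2 to 4.6%.
- Permutation test that re-estimates the weights: 3.2 to 5.0%.
- Weights and the same covariates together, with the default standard error: 7.5 to 9.2% in the settings tabulated.
- Weights entered as case counts: 7 to 22%. Unstabilised weights sum to about 2N = 104, so the standard error shrinks by about √(49/101) = 0.70.

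**The case against.** The strongest reply is that the plan names no variance estimator, weight type or software. A reader might infer that the standard error of every pilot comparison will be wrong, or that type I error will reach 10 to 20%. The documents support neither. The high figures need unstabilised weights to be entered as case counts, and nothing suggests that. A permutation test kept its level, so bad inference does not follow from weighting as such. The plan speaks of potential imbalance, which can be read as weighting only where imbalance appears.

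The precision loss is also small, and effective sample size overstates it. In a further simulation with 8 covariates and R² of 0.4, the mean effective sample size was 80% of N. The true standard errors of 0.239 (direct) and 0.254 (weighted) imply a relative efficiency of (0.239/0.254)² = 89%. Weighting usually still beats adjusting for the baseline outcome alone (0.226 against 0.245 at N = 52, 5 covariates, R² = 0.2), although with 8 covariates that gain is gone (0.246 against 0.244).

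If only completers are analysed, dropout may create imbalance that is not chance, so weights are not strictly idle. The simulations used a follow-up mean and normal outcomes, not three assessments with imputation, and viral load and percent adherence may be skewed. Finally, this is a pilot that itself concedes that power may be inadequate.

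All of this stands and limits the size of the point. None of it gives a reason to prefer weights to direct adjustment here. Direct adjustment held its level in every setting and had the smaller true SD at N = 52 to 60.

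**Conclusion.** The point holds as a cheap improvement to the analysis, not as a demonstrated error in it. With 60 randomised and about 52 analysed (60 if imputed), weighting is slightly less precise than putting the same covariates in the ANCOVA: true SD about 1 to 8% larger with 3 to 8 covariates. Because no standard error method is stated, a default one could be used, and it would be miscalibrated in a direction that depends on the covariates. It would be conservative with prognostic covariates (type I error about 1 to 4%, power down by 5 to 18 points at R² of 0.2 to 0.4 in the example) and mildly liberal with weak ones (about 7%).

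These sizes rest on the assumed number of covariates, R², baseline-outcome correlation and normal outcomes, none of which the documents give. The direction of the precision comparison was the same in every setting tried at N = 52 to 60.

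**What to change.** Replace the sentence on weights in the Data Analytic Plan with:

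> A small set of baseline covariates, fixed before outcome data are seen and used whether or not they look imbalanced (baseline value of the outcome; baseline log10 viral load where it is not the outcome; newly initiated on ART yes/no), will enter each ANCOVA.

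Viral load and the date of ART initiation are already on the Chart Review Data Abstraction Form (Appendix 2), so no new data are needed. The plan should state how the ART start date defines newly initiated.

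If weighting is kept, make it a sensitivity analysis only. Name its covariates, say how it is combined with the imputations, and use inference that re-estimates the weights, for example a permutation test. The bootstrap was conservative at this size. Do not rely on default standard errors from a model that both weights and adjusts.

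The cost is one sentence, a few degrees of freedom, and a small loss of precision if the covariates turn out not to be prognostic. As an upper guide, five useless covariates at N = 52 raised the mean standard error from 0.2434 to 0.2575, about 6%; the set proposed here is smaller.

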COVER PAGE

Official Title: A Text-Based Adherence Game for Young People Living with HIV in Ghana

NCT #: 1227391

Document Date: March 11, 2021

Document: Protocol

EXECUTIVE SUMMARY

- This study is funded by the National Institute of Mental Health (USA). It is a K23 Patient-Oriented Career Development Award received by Rhode Island Hospital (USA) to support the research described in this protocol and the training and career development activities of [name]. Grant#: K23 MH114632.
- [name] will serve as PI on the project alongside [name] (Co-PI) and [name] (Co-PI). Drs. [name] and [name] are medical doctors and researchers at the HIV Clinic of the Komfo Anokye Teaching Hospital (KATH) and faculty at the Kwame Nkrumah University of Science and Technology. [name] is a clinical psychologist and researcher at Rhode Island Hospital and the Alpert Medical School of Brown University (USA).
- The four-year study will develop a novel text message intervention for young people living with HIV, ages 18 to 24, who receive care at the KATH HIV Clinic. The intervention will be designed to help improve their adherence to HIV care (e.g., antiretroviral adherence). More so than other age groups, young people living with HIV are at risk for adherence problems and secondary HIV transmission.
- This is a *pilot* study focused on intervention development and testing the feasibility and preliminary efficacy of the text message intervention.
- The long-term goals of the project include:
 - Improve the health and well-being of young people living with HIV in Ghana and other countries in the region.
 - Use pilot data gathered from the study to apply for additional funding which could support a larger scale randomized controlled trial of the text message intervention.
 - Strengthen existing academic collaborations between US and Ghana-based research teams.

TITLE PAGE

Title of Protocol: A Text-Based Adherence Game for Young People Living with HIV

PI: [name], MBChB, DPDM, DTMH, FWACP, Department of Medicine, KATH. [name]. Ghana, West Africa, [name], [contact]

Co-PI: [name], MBChB, DPDM, FGCP, FWACP, Department of Paediatrics, KATH. [name]. Ghana, West Africa, [name], [contact]

Co-PI: [name], PhD, Bradley/Hasbro Children's Research Center, Rhode Island Hospital, [name], USA [contact], [contact]

Prior Scientific Review: No prior review conducted.

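### Does the power statement (small to medium effects with 52 participants) overstate what the pilot can detect?

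*Combined protocol and SAP*

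**What the plan says.** Under Hypothesis Two (Aim 2), the Data Analytic Plan predicts that "participants in the Text-Based Adherence Game will show at 6 and 12 months post-intervention" better adherence, attendance and biologic outcomes than controls. The method is "Repeated measures ANCOVAs will be used to test differences over time between study conditions on each outcome variable". The pilot section sets the assessments at baseline, 6 months and 12 months.

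The Power paragraph takes 60 enrolled, assumes at least 86% retention and so counts 52 for analysis. It cites G*Power 3 and states that "The model assumed 3 assessments with 52 individuals". It ends: "The analyses with alpha of 0.05 and power 0.80 will be able to detect small to medium effects". It gives no effect metric or number, no powered term, no correlation among assessments and no sphericity value.

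Earlier in the same paragraph the plan concedes that "there may not be adequate power to determine its efficacy; also, pilot studies are not designed to provide accurate estimates of effect sizes", adding that large trials should not be built on such estimates and that the pilot may show only a signal.

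**The concern.** Hypothesis Two is about game versus control at 6 and 12 months, so a reader may take the small-to-medium label as a standardised difference between arms, where 0.2 SD is conventionally small and 0.5 SD medium. Twenty-six per arm cannot reliably detect differences of that size in most scenarios.

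The sentence is also the plan's only statement of sensitivity, and one long-term goal in the Executive Summary is to "Use pilot data gathered from the study to apply for additional funding which could support a larger scale randomized controlled trial". If a funder or reader believed the pilot could detect a 0.2 to 0.5 SD difference, a null result might be taken as evidence against a worthwhile benefit.

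**Working it through.** **Inputs from the plan.** Enrolled 60; retention 86%; analysed N = 52; m = 3 assessments; alpha 0.05; power 0.80; repeated measures ANCOVA of differences over time between conditions.

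**Assumed, because the plan is silent.** 1:1 allocation (26 per arm); sphericity; a common correlation ρ of 0.3, 0.5 or 0.7, with 0.8 as a sensitivity value; complete data, with no loss from weighting or imputation.

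**Step 1: the plan's N.** 60 × 0.86 = 51.6, rounded to 52. It reproduces.

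**Step 2: the plan's label, group-by-time term.** Noncentral F with 2 and (52 − 2) × 2 = 100 degrees of freedom and noncentrality λ = f² × N × m / (1 − ρ) = 156 f² / (1 − ρ). Solving for 80% power gives f = 0.211, 0.178 and 0.138 at ρ = 0.3, 0.5 and 0.7. As a check at ρ = 0.5: 156 × 0.1784² / 0.5 ≈ 9.93. The other two correlations return the same λ. All three f values lie between 0.10 and 0.25.

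The label is fairly robust. With a sphericity factor of 0.75, f = 0.234, 0.198 and 0.153. At 0.5, the lowest possible value with three assessments, f = 0.271, 0.229 and 0.177, so only the first exceeds medium.

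**Step 3: the other candidate term.** For the average between-condition difference over all three assessments, λ = f² × N × m / (1 + 2ρ) with 1 and 50 degrees of freedom. This gives f = 0.289, 0.323 and 0.354, all above 0.25. The label therefore fits the group-by-time term, which is the one the method sentence describes.

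**Step 4: conversion to an arm difference.** Suppose the arms differ by 0, d, d at the three assessments. The deviations from the mean difference 2d/3 are −2d/3, d/3 and d/3. Half of each falls on each arm: d/3, d/6 and d/6 in size. The mean square is (d²/9 + d²/36 + d²/36) / 3 = d²/18, so d = f × √18 = 4.243 f. On this profile f = 0.10 is 0.42 SD and f = 0.25 is 1.06 SD.

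**Step 5: baseline-adjusted alternatives.** SE = √((2/26) × v), with 49 degrees of freedom. Here v = 1 − ρ² at 12 months and v = (1 + ρ)/2 − ρ² for the mean of both follow-ups.

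Detectable arm difference in SD at 80% power:

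| Test | ρ = 0.3 | 0.5 | 0.7 | 0.8 |
|---|---|---|---|---|
| Group-by-time, sustained effect | 0.90 | 0.76 | 0.59 | 0.48 |
| Group-by-time, effect building linearly, at month 12 | 1.03 | 0.87 | 0.68 | 0.55 |
| Baseline-adjusted, 12 months | 0.76 | 0.69 | 0.57 | 0.48 |
| Baseline-adjusted, mean of both follow-ups | 0.59 | 0.56 | 0.48 | 0.40 |

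At ρ = 0.3 / 0.5 / 0.7, power for a 0.5 SD difference is 32 / 43 / 66% (group-by-time, sustained), 46 / 53 / 70% (adjusted, 12 months) and 66 / 71 / 84% (adjusted mean). For 0.2 SD it is 9 to 22% across these three tests.

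**The case for a change.** The best case for a change is that the paragraph ends on an unqualified claim, "will be able to detect small to medium effects", while its caveat does not say which effects are out of reach. Even on the f scale, group-by-time power at exactly f = 0.10 is only 24 / 32 / 51% at ρ = 0.3 / 0.5 / 0.7. As an arm difference, 0.2 SD is out of reach on every test unless the correlation is about 0.96 or more. The remedy would cost one sentence.

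Three parts of this stand: the inputs are missing, the calculation cannot be repeated without guessing them, and a small arm difference is beyond this pilot. The claim of overstatement does not follow. It needs a conversion to a scale the plan does not use, plus an effect profile, an allocation ratio and a correlation that no document supplies. It also shifts with those choices. If the ANCOVA takes baseline as covariate and tests the mean of both follow-ups, the detectable difference is 0.48 to 0.59 SD, about medium. At ρ = 0.8 every sustained or adjusted figure falls below 0.5 SD.

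The feared misuse is addressed in the same paragraph, which says that power for efficacy may be inadequate and warns against basing large trials on pilot effect sizes. A replacement sentence built on a correlation chosen from outside would itself be unsupported.

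**Conclusion.** The power statement is terse but not shown to be wrong. For the group-by-time test that the plan describes, with 52 participants and three assessments, the detectable f is 0.14 to 0.21 at assumed correlations of 0.7 to 0.3, and small to medium is a fair name for that range. The equivalent sustained arm difference, 0.59 to 0.90 SD, rests on 1:1 allocation, sphericity, complete data and equal effects at both follow-ups. It is worth keeping in mind when a null result is read, but it corrects no figure in the plan.

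The calculation takes the pilot's size as given and asks what it could detect. The paragraph does not present 60 as derived from it, and no analysis or decision rule depends on it. Writing out the G*Power inputs would be tidier reporting, but the design, the tests and the conclusions would stay as they are. This is a gap in detail within a pilot that openly disclaims adequate power, so no change is called for.
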